Randomization. Eligible families will be randomly assigned to either the mindfulness enhanced mPRT or to pPRT as the control condition. The Randomization Module in REDCap will be completed by a research assistant, blind to the clinician completing the pre-treatment assessment. Groups will be matched on gender of caregiver to control for gender differences previously reported in parenting stress literature (Davis and Carter, 2008). Both caregivers are permitted to attend groups; however, one caregiver must identify as the primary reporter (i.e., individual who completes all self- and parent-report questionnaires, attends sessions regularly, and participates in all home videos).

If challenges with recruitment emerge, randomization rules may be adjusted. In this instance, once the period of recruitment has commenced and 3 or more families have completed the pre-assessment condition, a random number generator will be used to determine the group for the individuals.

Treatment (Appendix A). All families will receive the same dose of PRT parent training delivered in a previously studied package (e.g., Hardan et al., 2014) that includes 16 hours of group sessions and 4 hours of individual sessions, delivered over a 12-week timeframe. The format for teaching PRT techniques and abilities will be replicated from Hardan et al. (2014), who adapted the material from the manual, “How to Teach Pivotal Behaviors to Children with Autism” (Koegel et al., 1989) and has been previously implemented in a feasibility study by the current researchers.

Additionally, all parents will receive 6 hours total of group supplemental treatment that specifically targeted parenting stress either by mindfulness-based techniques or by psychoeducation (depending on random assignment). Materials from the psychoeducation group include didactic training on a variety of topics focusing on the parent, child and family outcomes. For example, literature on general parenting stress as well as parenting stress in parents of children with ASD was one topic presented in an informational manner, without providing instruction regarding specific skills training.

The mindfulness-enhanced treatment, on the other hand, provides specific skills as well as didactic information about applying mindfulness to the parenting role. Components from ACT as well as Mindful Parenting will be incorporated into the weekly sessions in a manner that applied the mindfulness skills to the newly learned PRT skills.

Measures

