Parent Feelings Questionnaire (PFQ; Deater-Deckard, 2000). The PFQ (Appendix F) consists of 24 items rated on a 5-point Likert-type scale and measured self-report of personal negative and positive feelings toward the child participating in treatment. The items include statements about feelings toward the child participating in the study. For example, “Sometimes my child can really test my patience” and “I find it easy to praise and compliment my child, especially for good behavior” are questions from the negativity sub-scale and positivity subscale respectively. Previous literature demonstrates good internal consistency for both the positivity scale (Cronbach’s alpha = .88) and negativity scale (Cronbach’s alpha = .90; Wang, Deater-Deckard, & Bell, 2013). The positivity scale will be used to assess group differences over time.

Positive and Negative Affect Schedule (PANAS; Crawford & Henry, 2004). The PANAS (see Appendix G) is a reliable and valid measure of positive and negative affect in adults. Previous literature demonstrates good internal consistency for the Positive Affect scale ($\alpha = .89$) and .Negative Affect scale ($\alpha = .85$). For the current study, the instructions for the PANAS were adapted to assess level of parent affect during parent-child interactions in clinic (i.e., during each SLO). The positive affect scale will be used to measure changes over time.

Parent mindfulness.

Five Facet Mindfulness Questionnaire (FFMQ; Baer et al., 2006). The FFMQ (Appendix H) is a 39-item self-report measure that assesses one’s general propensity towards mindfulness in daily life. The FFMQ consists of 5 subscale scores (i.e., non-reactivity to inner experience, observing, describing, acting with awareness, and non-judging of inner experience) that load onto a total mindfulness score. Parents endorse statements on a 5-point Likert scale ranging from

1 (Never or Rarely True) to 5 (Very Often or Always True), with higher scores reflecting increased levels of mindfulness.

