Acceptance and Action Questionnaire-II (AAQ-II; Bond et al., 2011). The AAQ-II (Appendix I) is a seven-item measure designed to capture a person's level of experiential avoidance, where each item is ranked on 7 point scale ranging from "never true" to "always true". Higher scores on the measure reflect increased levels of experiential avoidance, the antithesis of psychological flexibility. The AAQ-II demonstrates good internal consistency (i.e., ranging from .78 to .87 across three samples) and acceptable test-retest reliability (i.e., .78 - .88). The AAQ-II will be administered at all time points.

Child problem behavior. The Child Behavior Checklist for Ages 1.5-5 (CBCL/1.5-5; Achenbach & Rescorla, 2001) is a parent report measure on child emotional and behavioral characteristics. Previous research suggests a bidirectional relationship between parent stress and child problem behaviors. Although the treatments in the current study focus on increasing child utterances and reducing parenting stress, changes in child problem behavior are also included to better understand baseline differences and change because of treatment. The CBCL demonstrates good internal consistency in general populations (.89 for internalizing and .92 for externalizing; Achenbach & Rescorla, 2001) as well as ASD specific populations (.80 for internalizing, .90 for externalizing; Pandolfi, Magyar, & Dill, 2009).

Statistical Analysis Plan

All data will be checked for normality, skewness, and kurtosis. In the case of small sample size and non-normal distributions, non-parametric analyses will be used to compare groups and changes over time.

Treatment feasibility and acceptability.

Parental adherence to treatment. Retention rate will be calculated by dividing the number of participants who were considered treatment completers by the total number of participants who were randomly assigned to a group. Because weekly videos were a crucial and core component of the PRT treatment package, the total number of videos submitted by parents will be calculated as a measure of adherence. Finally, parent weekly ratings of the amount of time spent implementing PRT skills in the home environment will be averaged to compare between groups.

Treatment satisfaction. The sections on perceived level of difficulty and helpfulness for PRT strategies will be averaged separately for each group.

Treatment efficacy and exploratory analyses.

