Group differences. Pending anticipated non-normal distributions of the small samples, Mann-Whitney U tests will be used to make baseline comparisons to compare independent samples (i.e., completers versus non-completers; mPRT versus pPRT). G*Power3 (Faul, Erdfelder, Lang, & Buchner, 2007) power analyses will be completed to evaluate the size of effect one can be expected to obtain given the obtained sample size, and $\alpha = .05$. A sample size of 95 will be necessary to detect a large effect ($r = .5$). Group comparisons will also be made at post-treatment to analyze differences in parent fidelity of PRT techniques and treatment satisfaction. To calculate effect size, the following formula will be ($r = Z/\sqrt{N}$). The

interpretation of r values are as follows: .5 = large effect, .3 = medium effect, .1 = small effect (Coolican, 2009; Fritz, Morris, & Richler, 2012).

In addition, to test within-group changes, non-parametric Wilcoxon Signed Rank Test (equivalent to a dependent t -test) will be used to compare baseline and endpoint/follow-up scores for each group across variables of interest. A sample size of 27 will be necessary to detect a large effect ($r = .5$) and 648 for a small effect ($r = .1$). Due to low power, effect sizes will also be calculated when determining change as a result of treatment.

Single-Subject Analyses. In addition to group change over time, individual level change will be calculated for parenting stress, parent mindfulness, and parent positive feelings toward child using Reliable Change Index (RCI; Jacobson & Truax, 1991). RCIs will be calculated to determine the magnitude of change needed to show meaningful change above and beyond standard error. RCI calculations will be completed by dividing the difference of scores between two timepoints (i.e., either pre-treatment and post-treatment or pre-treatment and follow-up), divided by the standard difference, which includes test-retest reliability and standard deviation of the original measure. RCI values above 1.96 are suggested to infer statistically significant and meaningful change. The test-retest reliabilities and standard deviations used to compute the S_{diff} score will be obtained from the literature. If test-retest reliability was not previously reported in literature, then Cronbach's alpha was used (from the literature).

Table 1
Assessment Schedule

Construct/ Measure	Pre-Tx	Mid	Weekly	Post-Tx	Follow-up
Sample Characterization					
ADOS-2	X				

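### After baseline, the SAP plans no mPRT versus pPRT test or estimate for parenting stress, the outcome named in the trial's title

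*Combined protocol and SAP*

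**What the plan says.** The title names parenting stress as the outcome. Under Procedure, Randomization: "Eligible families will be randomly assigned to either the mindfulness enhanced mPRT or to pPRT as the control condition". Under Treatment, both arms get the same PRT package, and "all parents will receive 6 hours total of group supplemental treatment that specifically targeted parenting stress either by mindfulness-based techniques or by psychoeducation". PSI-4, APSI and SUPSS all fall under the Measures heading for primary outcome variables.

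The SAP's arm comparisons are these:

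- Baseline Mann-Whitney tests, mPRT versus pPRT (Group differences).
- Home practice: "parent weekly ratings of the amount of time spent implementing PRT skills in the home environment will be averaged to compare between groups" (Parental adherence to treatment).
- After treatment: "Group comparisons will also be made at post-treatment to analyze differences in parent fidelity of PRT techniques and treatment satisfaction" (Group differences).

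For change over time, the Wilcoxon signed-rank test "will be used to compare baseline and endpoint/follow-up scores for each group across variables of interest". The same paragraph adds that "effect sizes will also be calculated when determining change as a result of treatment". Under Single-Subject Analyses, "individual level change will be calculated for parenting stress, parent mindfulness, and parent positive feelings toward child using Reliable Change Index".

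In Measures, the Parent Feelings Questionnaire (PFQ) entry says: "The positivity scale will be used to assess group differences over time". The SAP assigns no test to this, and the stress measures have no matching sentence.

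**The concern.** Because both arms receive the same PRT training and equal hours of a supplement aimed at stress, only the mPRT versus pPRT contrast isolates mindfulness. Change within an arm mixes any mindfulness effect with the shared PRT effect, the passage of time and regression to the mean. An individual Reliable Change Index has the same limit.

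The plan therefore randomises to ask a question that its analysis does not answer. Two things follow. Within-arm change may be reported as an effect of treatment, which the SAP's own wording invites. And a result that is significant in one arm but not in the other may be taken as a difference between arms, which it does not show. If an arm comparison is added once data are seen, the choice among three stress measures, several time points, and change or endpoint scores is unprotected.

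**Working it through.** **1. Planned analyses set side by side**

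| Analysis | Compares arms? | Covers stress after baseline? |
|---|---|---|
| Mann-Whitney at baseline | Yes | No |
| Home-practice ratings | Yes | No |
| Post-treatment group comparisons | Yes | No: parent fidelity and satisfaction only |
| Wilcoxon signed-rank | No, run in each arm | Yes, if stress is a variable of interest (not listed; I read it so) |
| Effect sizes for change | No, stated with the within-arm test | Within arm only |
| Reliable Change Index | No, per caregiver | Yes, individually |

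No row has Yes for both.

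**2. The plan's sample-size figures.** The SAP gives 95 for the between-group comparison and 27 and 648 for the within-group test. With effects of 0.5 and 0.1 taken as standardised differences, one-sided .05, 80% power and normal data, the within-group figures come out at 28 and 649, within one of those stated. The same settings give 106 for the between-group comparison, not 95. That is a separate matter, and nothing below depends on it.

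**3. What two within-arm tests show when the arms do not differ.** Assumptions: normal change scores with SD 1, the same standardised gain dz in both arms, exact two-sided Wilcoxon at .05. The rejection regions are W ≤ 0 for n = 6 (level 2 × 1/64 = .031), W ≤ 2 for n = 7 (2 × 3/128 = .047) and W ≤ 3 for n = 8 (2 × 5/256 = .039). The documents give N = 15 but no allocation ratio, so the splits are assumed.

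The arms are independent, so P(mPRT significant, pPRT not) = p(mPRT) × [1 − p(pPRT)]. At 8 v 7 and dz = 0.8, simulated within-arm power is .429 (n = 8) and .407 (n = 7), giving .429 × .593 = .254. The larger simulation (400,000 trials per setting) gives .257. Its full results:

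| mPRT v pPRT | dz 0.2 | 0.5 | 0.8 | 1.0 | 1.2 |
|---|---|---|---|---|---|
| 8 v 7 | 5% | 16% | 26% | 27% | 22% |
| 7 v 8 | 6% | 15% | 23% | 22% | 17% |
| 7 v 6 (two lost) | 6% | 17% | 30% | 37% | 37% |
| 6 v 7 (two lost) | 4% | 9% | 14% | 15% | 14% |

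Counting either arm as the lone significant one, the 8 v 7 figures are 11, 31, 49, 49 and 38%. These are frequencies of a misleading pattern, not the error rate of a planned test.

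**4. What the missing contrast would deliver.** Exact two-sided Mann-Whitney on change, 8 v 7: reject at U ≤ 10, level .040.

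- Power at d = 0.5, 0.8, 1.0, 1.2 and 1.7 (SD of change): 12, 25, 37, 51 and 81%. At 7 v 6: 10, 20, 30, 41 and 71%.
- Median full width of the Hodges-Lehmann 95% interval: 2.36 SD of change (8 v 7), 2.66 SD (7 v 6).
- Smallest significant effect size at 8 v 7: Z = (28 − 10)/√(56 × 16/12) = 18/8.641 = 2.083, so r = 2.083/√15 = .54. This exceeds the .5 that the SAP calls large.
- If each arm is one treatment group, the true null rejection rate is about 7% at an assumed ICC of .05 and 11% at .10.

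**The case against.** The best reply is that the contrast is under-specified rather than absent. The SAP's opening paragraph says that non-parametric methods will serve both group comparisons and change over time. The efficacy section is headed Group differences, names Mann-Whitney for mPRT versus pPRT, gives r = Z/√N, and quotes a sample size that would make little sense for baseline checks alone. An efficacy contrast was probably intended.

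Intent can be inferred from this, but no analysis can. The opening sentence picks a class of test and names no outcome, time point or estimate. Mann-Whitney is tied to baseline, the later comparisons are listed without stress, and the formula for r follows that list.

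Three further points stand in part:

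- The simulation is illustrative. It assumes normal change scores, although the SAP expects non-normal data, and two-sided tests, although the SAP states no sidedness. No sentence says that the two p-values will be compared. The concern rests on the text and does not need the simulation.
- Several outcomes are listed as primary without ranking, so the choice of lead stress measure belongs to the sponsor.
- At N = 15 the added test will seldom reject. That is a reason to report an estimate with its interval, not to omit the randomised comparison.

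**Conclusion.** The concern holds and should be fixed before analysis. As written, the SAP yields no randomised estimate for the title outcome and attributes within-arm change to treatment. This conclusion comes from the wording and depends on no assumed figure, apart from reading stress as one of the Wilcoxon variables. If it is not one, stress has even less analysis.

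On size: with equal true gains, mPRT alone is significant in 5 to 27% of trials at 8 v 7, and in 4 to 37% over the splits tried. A direct Mann-Whitney test on change rejects in 4.0% at 8 v 7 if parents are independent. Arm sizes, gains, dropout, ICC, normality and two-sided testing are all assumptions.

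**What to change.** Add to Group differences text such as:

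> The efficacy comparison is mPRT versus pPRT on change in PSI-4 Child Domain from pre- to post-treatment, by two-sided exact Mann-Whitney test at .05, with the Hodges-Lehmann shift, its 95% CI and r = Z/√N. The same estimate and interval will be given, without confirmatory claim, for APSI, SUPSS and PFQ positivity at post-treatment and for all four measures at follow-up. Within-arm Wilcoxon tests and RCIs are descriptive and do not support statements about mPRT versus pPRT.

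The sponsor may name another stress measure as lead, provided it does so before data are seen. The text should also state:

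- which randomised caregivers are analysed, and how missing scores are handled;
- how the exact test treats ties;
- the number of treatment groups per arm, and that the test and interval assume independent parents.

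Remove the words that attribute change to treatment from the within-group paragraph and from the PSI-4 entry in Measures.

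The cost is SAP wording and a few lines of analysis. Table 1 already schedules all four measures at pre-treatment, post-treatment and follow-up. The price is candour: 80% power needs d of about 1.7, the interval will be wide, and the result will look less favourable than within-arm p-values. It should be presented as an estimate, not a definitive test.

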Parents will engage in a 15-minute task with their child to measure baseline levels of child utterances and baseline fidelity of PRT techniques. This task is called the Structured Laboratory Observation (SLO) and will be modeled from Hardan et al. (2014). During the first five minutes, parents will be instructed to sit quietly and watch their child play (i.e., do not initiate interactions; however, parents can respond if child initiates). This period allows the child to become acquainted with the room and materials. Then, parents will be instructed to elicit language from the child for 10 minutes, using whatever strategies they want. Immediately following the SLO, parents will be asked to provide self-reported perceptions of positive and negative mood and stress levels during the parent and child interaction. In addition to measuring baseline child utterances with a caregiver, all children will engage in a 10-minute SLO with a trained PRT clinician to control for baseline levels of fidelity of PRT techniques. Finally, parents will complete paperwork to determine demographic information, child language and social behaviors, as well as levels of parenting stress, parent feelings toward child, and mindfulness.

Data will be collected over the course of four time points (pre-treatment, mid-treatment, post-treatment, 3-month follow-up) and weekly. See Table 1 for the complete battery at each timepoint. All questionnaire data will be collected either via paper and pencil or sent from and stored electronically through an online system called Research Electronic Data Capture (REDCap; Harris, Taylor, Thielke, Payne, Gonzalez, & Conde, 2009), hosted at Virginia Tech. REDCap is a secure, web-based application designed to support data collection for research studies. Weekly measures include a 10-minute home video of a participating parent interacting with his or her child while implementing PRT strategies and eliciting language. These videos will

be used in treatment to review strengths, areas of growth, and barriers encountered in the naturalistic settings as well as in research to monitor changes in child utterances and percentage of fidelity of implementing PRT strategies. In an effort to decrease demands from parents, we will provide families with Android tablets and instructions on how to upload the videos.

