
Eligibility and sample characterization.

Autism Diagnostic Observation Schedule, Second Edition (ADOS-2; Lord et al., 2012).

The ADOS-2 is a semi-structured, observational assessment of ASD characteristics and is one of the gold standard tools used to assess social communicative and repetitive behaviors in children who are suspected of having ASD. The ADOS-2 consists of multiple modules, which are determined by age and language ability. The Toddler Module and Module 1 are administered to children with no or little verbal language and Module 2 is used for children with phrase, but not verbally fluent, speech. The ADOS-2 demonstrates moderate to high levels of internal consistency, moderate test-retest reliability, and acceptable interrater reliability (McCrimmon & Rostad, 2014).

Mullen Scales of Early Learning (MSEL; Mullen, 1995). The MSEL measures developmental functioning for young children, specifically in visual, linguistic, and motor domains. Additionally, the MSEL distinguishes between receptive and expressive language abilities. The MSEL demonstrates good internal consistency and high test-retest reliability (Mullen, 1995).

Treatment feasibility and acceptability.

Parental adherence to treatment. Treatment adherence will be measured by the number of weekly videos provided, as these were crucial components of treatment in regard to teaching and providing feedback. Parents will also receive weekly questionnaires inquiring how often they practiced PRT techniques during the past week and ranged from 0 (Not at all) to 4 (Every day). Averages will be calculated accounting for the amount of questionnaires they completed.

Treatment satisfaction. The participants' satisfaction with the treatment components will be assessed at the post-treatment time point. First, participating caregivers rate their satisfaction with the overall program. Then, parents rate their perceived difficulty and helpfulness of the treatment components (i.e., PRT specific concepts as well as the individual's assigned supplemental group). The satisfaction survey also includes open-ended responses to better understand the components that parents viewed as most helpful, least helpful, and recommendations for future groups.

Treatment efficacy: Primary outcome variables.

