Parent fidelity of PRT implementation (Appendix D). Parent fidelity of PRT

implementation will be coded by trained undergraduate research assistants using *Noldus The Observer XT* to measure changes in level of fidelity in-laboratory semi-structured tasks and in-home naturalistic environments over the course of treatment. All videos, including SLOs at all 4 timepoints as well as weekly videos (averaged for weeks 1-2 and weeks 9-10) will be coded by two research assistants separately (i.e., each research assistant coded all the videos separately). After videos were double-coded, the two research assistants will meet together to complete final consensus coding. All research assistants will attend group training in behavioral coding, behavioral management, and PRT techniques; they will attain at least 80% fidelity with two sample videos coded by PhD and master's level clinicians who were certified in PRT. Standardized measures of PRT fidelity (e.g., Bryson, Koegel, Koegel, Openden, Smith, & Neft, 2007; Minjarez et al., 2011) will be adapted for the current project to accommodate measurement every 30 seconds (as opposed to 1- or 2-minute intervals).

Fidelity of PRT implementation will include 5 total over-arching techniques (i.e., shared control, providing clear opportunities, interspersing maintenance trials, reinforcing attempts, and contingent/natural reinforcement of appropriate behavior), which could be further divided into 10 total components (i.e., following child's lead/child choice, natural reinforcer, attending to task, clear instructions, maintenance, task variation, natural, immediate, appropriate and attempts). The *Noldus* system will be automatically programmed to stop a video after every 30 seconds and prompt the research assistant to input fidelity information for all 10 components in a binary form (i.e., parent either achieved correct performance of component for the entire interval or did not, coded as 1 or 0 respectively). Total correct percentages will be calculated for each component and then averaged over the number of intervals to create a final correct percentage for total PRT

fidelity. Because final percentages will be individually calculated based on the total time they were coded, videos that range in length from 5 minutes to 10 minutes will be used for the current set of analyses.

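### The post-treatment between-arm comparison of parent PRT fidelity states no adjustment for the baseline fidelity the trial collects; a one-covariate rank analysis is a cheap, low-priority improvement

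*Combined protocol and SAP*

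**What the plan says.** Parent fidelity of PRT implementation is described under the Measures heading "Treatment efficacy: Primary outcome variables". For this outcome the Statistical Analysis Plan (Group differences) states: "Group comparisons will also be made at post-treatment to analyze differences in parent fidelity of PRT techniques and treatment satisfaction". The sentence names no test and no covariate. Mann-Whitney U is the only between-arm test named anywhere. It is named for baseline comparisons, so its use at post-treatment is inferred from context.

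The baseline score exists. The Procedure section says: "Parents will engage in a 15-minute task with their child to measure baseline levels of child utterances and baseline fidelity of PRT techniques". The parent-fidelity section says what is coded: "All videos, including SLOs at all 4 timepoints as well as weekly videos". Table 1 has no row for parent fidelity, but these two sections are explicit.

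Elsewhere the SAP uses baseline in two ways: a baseline comparison of the arms, and a Wilcoxon signed rank test that "will be used to compare baseline and endpoint/follow-up scores for each group across variables of interest". Effect size is r = Z/√N, and the stated "interpretation of r values are as follows: .5 = large effect, .3 = medium effect, .1 = small effect".

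**The concern.** Randomisation matches the arms on caregiver gender only, so nothing in the design balances starting fidelity. With 15 dyads the arms can easily differ at baseline by chance. Part of that difference carries into the post-treatment scores, to the extent that baseline and post-treatment fidelity are correlated. The baseline comparison and the within-arm tests would reveal such a gap, but they do not take it out of the between-arm contrast or out of its r. This matters because the SAP acknowledges low power and turns to effect sizes to judge change, so a displaced r could be graded small, medium or large on the strength of where the arms started.

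**Working it through.** **Inputs.** From the documents: 15 randomised (read as 15 dyads), α = .05, r = Z/√N, and grades .1/.3/.5. Not in the documents, so assumed: a 7 v 8 split, two-sided testing, a baseline-to-post correlation ρ from 0 to .7, independent parents, and 6 v 6 as a dropout case.

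**The plan's own figure.** The SAP gives N = 95 for the between-group test at r = .5. It does not reproduce on a reading consistent with its paragraph. At 80% power with a normal parent distribution, .5 read as d gives 106 (one-sided) or 134 (two-sided); read as r it gives 22 or 28. Nothing below uses it.

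**Step 1: how often a gap arises.** The SE of the baseline difference is √(1/7 + 1/8) = 0.518 SD. Then 0.75/0.518 = 1.45, so P(|gap| ≥ 0.75 SD) = .147.

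**Step 2: behaviour with no treatment effect.** Bivariate normal simulation, 200,000 trials per setting. Exact Mann-Whitney size by enumeration is .0401. The Quade test is calibrated to the same size.

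| ρ | Mann-Whitney false positives, gap ≥ 0.75 / smaller | Quade, same | Mean r towards arm ahead (gap ≥ 0.75), unadjusted / adjusted | P(r ≥ .3) that way, unadjusted / adjusted |
|---|---|---|---|---|
| .3 | 6.0% / 3.6% | 2.3% / 4.3% | .14 / .01 | .25 / .11 |
| .5 | 9.5% / 3.1% | 2.5% / 4.3% | .23 / .01 | .37 / .12 |
| .7 | 14.7% / 2.2% | 2.9% / 4.2% | .32 / .02 | .52 / .14 |

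The two Mann-Whitney columns average back to its overall size. At ρ = .5, .147 × .095 + .853 × .031 = .014 + .026 = .040.

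**Step 3: all randomisations together.** The null chance of |r| ≥ .3 is .23 unadjusted and .26 adjusted. The benefit is therefore conditional on a gap.

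**Step 4: power at matched size.** r = .5 taken literally gives d = 2r/√(1 − r²) = 1/√.75 = 1.155.

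| Scenario | Mann-Whitney | Quade at ρ = 0 / .3 / .5 / .7 |
|---|---|---|
| d = 1.155, 7 v 8 | .48 | .44 / .48 / .54 / .67 |
| d = 0.5, 7 v 8 | .120 | .113 / .120 / .135 / .173 |
| d = 1.155, half of parents at baseline floor | .48 | .45 / .46 / .52 / .62 |
| d = 1.155, 6 v 6 | .38 | .35 / .37 / .42 / .54 |
| d = 1.155, 6 v 6 with floor | .38 | .35 / .37 / .40 / .49 |

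The break-even agrees with the variance ratio (1 − ρ²)(N − 3)/(N − 4). At N = 15 this is 12/11 = 1.09 at ρ = 0, .99 at .3, .82 at .5 and .56 at .7, and it equals 1 at ρ = √(1/12) = .29.

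**Step 5: scale of adjusted r.** At a true d = 0.5, mean r is .23 unadjusted but .25 adjusted at ρ = .5 and .29 at ρ = .7. P(r ≥ .3) moves from .39 to .44 and .51. Adjusted r is not on the scale for which the grades were set.

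**The case against.** The strongest case is that this is a preference. An unadjusted rank comparison is conventional in a randomised pilot of this size, and it is valid. The benefit depends on a correlation the documents do not give. That correlation may be low: at baseline parents elicit language "using whatever strategies they want", before any training, and scoring is strict ("parent either achieved correct performance of component for the entire interval or did not, coded as 1 or 0 respectively"), so a floor is plausible. The larger power gains need d = 1.155, yet both arms receive the same PRT dose and differ only in the supplement aimed at parenting stress, so a small fidelity difference is plausible. The 0.75 SD cut-off is also a choice. At 0.5 SD, which about 33% of randomisations reach, Mann-Whitney false positives are 4.5/5.0/6.9/8.9% at ρ = .2/.3/.5/.7, so there is no inflation above 5% at ρ of .3 or below. Finally, the planned baseline comparison would show readers a gap.

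Most of this stands, and it is why the priority is low. What does not answer the point is the visibility of a gap, because seeing it does not remove it from the contrast or from r. Nor does anything else in the plan. The clinician-child observation, described as a control for baseline fidelity, concerns child utterances and enters no parent-fidelity analysis. The reliable change analysis covers stress, mindfulness and positive feelings only.

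A reader might infer that the planned test is biased or exceeds its error rate. It does not: excess false positives after a large gap are offset by fewer in the other 85% of randomisations. A reader might also infer that adjustment would make the comparison adequately powered, or would make spurious medium effects rarer overall. Steps 3 and 4 show neither.

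**Conclusion.** The point holds as a missed improvement. No baseline term is stated for an outcome under the primary heading, although the covariate is already collected. In roughly one randomisation in seven the unadjusted result would lean noticeably towards the arm that started ahead; adjustment removes most of that lean (with half of parents at floor, null mean r of .03/.05/.07 remains at ρ = .3/.5/.7). The effect on power is mixed. At d = 1.155 it is about −4 points at ρ = 0, nil at .3, +6 at .5 and +19 at .7. At d = 0.5 it gains at most 1.5 points up to ρ = .5.

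This rests on 15 dyads split 7 v 8, Mann-Whitney as the intended test, an assumed range for ρ, and independence between parents, although treatment is delivered in groups. Both tests use ranks, so monotone skew would not change the null results.

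**What to change.** In the SAP under Group differences, before outcome data are seen:

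- State that post-treatment parent SLO fidelity is compared between arms with baseline parent-SLO fidelity as the single covariate. Name one method: Quade rank ANCOVA, or a permutation test on the baseline-adjusted ranks. The permutation re-allocations must respect the randomisation scheme actually used, including the caregiver-gender matching and any change of rules if recruitment is difficult.
- Define adjusted r = Z/√N, with Z the standardised permutation statistic of the adjusted ranks, or the signed normal deviate of the two-sided p-value. Label it baseline-adjusted and report the unadjusted Mann-Whitney r beside it, because the .1/.3/.5 grades belong to the unadjusted scale.
- Keep Mann-Whitney for treatment satisfaction, which has no baseline.
- Do not substitute change scores. At d = 0.8 a Mann-Whitney test on change has power .14 to .19 for ρ up to .3, against about .25 on post-treatment scores.

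Pre-specification matters because adjusting only after the baseline comparison shows a gap would be data-driven.

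The cost is SAP wording, with no new data. The plan should also state the downsides: ρ is unknown; power falls slightly if it is low; the overall null chance of |r| ≥ .3 rises from about .23 to .26; gains shrink with a baseline floor or dropout; and adjustment does not repair selective dropout. Quade's nominal size runs slightly high (.050 to .053 at 7 v 8, up to .055 at 6 v 6). The permutation version held .049 to .052 over all 6,435 unrestricted 7 v 8 allocations; a set restricted by the matching was not simulated.
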